7.4. Gilead Reporting Requirements

Depending on relevant local legislation or regulations, including the applicable US FDA Code of Federal Regulations, the EU Clinical Trials Directive (2001 / 20 / EC) and relevant updates, and other country-specific legislation or regulations, Gilead may be required to expedite to worldwide regulatory agencies reports of SAEs, serious adverse drug reactions (SADRs), or SUSARs. In accordance with the EU Clinical Trials Directive (2001 / 20 / EC), Gilead or a specified designee will notify worldwide regulatory agencies and the relevant IEC in concerned Member States of applicable SUSARs as outlined in current regulations.

Assessment of expectedness for SAEs will be determined by Gilead using reference safety information specified in the investigator's brochure. Assessment of expectedness for adalimumab SAEs will be determined by the adalimumab EU SmPC (SmPC Section 4.8) or relevant local label as applicable.

All investigators will receive a safety letter notifying them of relevant SUSAR reports associated with any study drug. The investigator should notify the IRB / IEC of SUSAR reports as soon as is practical, where this is required by local regulatory agencies, and in accordance with the local institutional policy.

7.5. Clinical Laboratory Abnormalities and Other Abnormal Assessments as Adverse Events or Serious Adverse Events

Laboratory abnormalities are usually not recorded as AEs or SAEs. However, laboratory abnormalities (e.g. clinical chemistry, hematology, and urinalysis) independent of the underlying medical condition that require medical or surgical intervention or lead to investigational medicinal product interruption or discontinuation must be recorded as an AE or SAE, as applicable. In addition, laboratory or other abnormal assessments (e.g. ECG, X-rays, vital signs) that are associated with signs and / or symptoms must be recorded as an AE or SAE if they meet the definition of an AE (or SAE) as described in Sections 7.1.1 and 7.1.2. If the laboratory abnormality is part of a syndrome, record the syndrome or diagnosis (i.e. anemia) not the laboratory result (i.e. decreased hemoglobin).

Adverse events will be coded using the most recent version of the Medical Dictionary for Regulatory Activities (MedDRA). Severity should be recorded and graded according to the CTCAE Version 5.0, which can be found at:

https://ctep.cancer.gov/protocolDevelopment/electronic_applications/docs/CTCAE_v5_Quick_Reference_8.5x11.pdf

For AEs associated with laboratory abnormalities, the event should be graded on the basis of the clinical severity in the context of the underlying conditions; this may or may not be in agreement with the grading of the laboratory abnormality.

All clinical and clinically significant laboratory toxicities will be managed according to uniform guidelines detailed in [Appendix 4](#) and as outlined below.

7.5.1. Grades 1 and 2 Laboratory Abnormality or Clinical Event

- For study specific interruption and stopping criteria, please refer to Section 3.5 (Criteria for Interruption or Discontinuation of study treatment)

7.5.2. Grades 3 Laboratory Abnormality or Clinical Event

- For study specific interruption and stopping criteria, please refer to Section 3.5 (Criteria for Interruption or Discontinuation of study treatment)
- For Grades 3 Laboratory Abnormality or Clinical Event not specified in Section 3.5, the following toxicity management guidelines apply:
 - For Grade 3 clinically significant laboratory abnormality or clinical event, study drug may be continued if the event is considered to be unrelated to study drug.
 - For a Grade 3 clinical event, or clinically significant laboratory abnormality confirmed by repeat testing, that is considered to be related to study drug, investigational medicinal product should be withheld until the toxicity returns to \leq Grade 2.
 - If a laboratory abnormality recurs to \geq Grade 3 following re-challenge with study drug and is considered related to study drug, then study drug should be permanently discontinued and the subject managed according to local clinical practice. Recurrence of laboratory abnormalities considered unrelated to study drug may not require permanent discontinuation.

7.5.3. Grades 4 Laboratory Abnormality or Clinical Event

- For study specific interruption and stopping criteria, please refer to Section 3.5 (Criteria for Interruption or Discontinuation of study treatment)
- For Grade 4 Laboratory Abnormality or Clinical Event not specified in Section 3.5, the following toxicity management guidelines apply:
 - For a Grade 4 clinical event or clinically significant Grade 4 laboratory abnormality confirmed by repeat testing that is considered related to study drug, study drug should be permanently discontinued and the subject managed according to local clinical practice. The subject should be followed as clinically indicated until the laboratory abnormality returns to baseline or is otherwise explained, whichever occurs first. A clinically significant Grade 4 laboratory abnormality that is not confirmed by repeat testing should be managed according to the algorithm for the new toxicity grade.
- Study drug may be continued without dose interruption for a clinically non-significant Grade 4 laboratory abnormality (e.g. Grade 4 creatine kinase (CK) after strenuous exercise or triglyceride elevation that is non-fasting or that can be medically managed) or a clinical event considered unrelated to investigational medicinal product.

7.6. Toxicity Management

Treatment-emergent toxicities will be noted by the investigator and brought to the attention of the Gilead Sciences Medical Monitor or designee, who will have a discussion with the investigator and decide the appropriate course of action. Whether or not considered treatment-related, all subjects experiencing AEs must be monitored periodically until symptoms subside, any abnormal laboratory values have resolved or returned to baseline levels or they are considered irreversible, or until there is a satisfactory explanation for the changes observed.

Any questions regarding toxicity management should be directed to the Gilead Sciences Medical Monitor or designee.

7.6.1. Thromboembolic Events

Subjects experiencing a thromboembolic event should be evaluated for the overall risk of recurrent thromboembolism and referred to a specialist for further testing as appropriate (including but not limited to evaluation for an underlying inherited hypercoagulable state).

7.7. Special Situations Reports

7.7.1. Definitions of Special Situations

Special situation reports include all reports of medication error, abuse, misuse, overdose, occupational exposure, drug interactions, exposure via breastfeeding, unexpected benefit, transmission of infectious agents via the product, counterfeit or falsified medicine, and pregnancy regardless of an associated AE.

Medication error is any unintentional error in the prescribing, dispensing, preparation for administration or administration of an investigational product while the medication is in the control of a health care professional, patient, or consumer. Medication errors may be classified as a medication error without an AE, which includes situations of missed dose; medication error with an AE; intercepted medication error; or potential medication error.

Abuse is defined as persistent or sporadic intentional excessive use of an investigational product by a subject.

Misuse is defined as any intentional and inappropriate use of an investigational product that is not in accordance with the protocol instructions or the local prescribing information.

An overdose is defined as an accidental or intentional administration of a quantity of an investigational product given per administration or cumulatively which is above the maximum recommended dose as per protocol or in the product labeling (as it applies to the daily dose of the subject in question). In cases of a discrepancy in drug accountability, overdose will be established only when it is clear that the subject has taken the excess dose(s). Overdose cannot be established when the subject cannot account for the discrepancy except in cases in which the investigator has reason to suspect that the subject has taken the additional dose(s).

Occupational exposure is defined as exposure to an investigational product as a result of one's professional or non-professional occupation.

Drug interaction is defined as any drug/drug, drug/food, or drug/device interaction.

Unexpected benefit is defined as an unintended therapeutic effect where the results are judged to be desirable and beneficial.

Transmission of infectious agents is defined as any suspected transmission of an infected agent through a GSI investigational product.

Counterfeit or falsified medicine is defined as any investigational product with a false representation of: a) its identity, b) its source, or c) its history.

7.7.2. Instructions for Reporting Special Situations

7.7.2.1. Instructions for Reporting Pregnancies

The investigator should report pregnancies in female study subjects that are identified after initiation of study medication and throughout the study, including the post study drug follow-up period, to Gilead PVE using the pregnancy report form within 24 hours of becoming aware of the pregnancy.

Refer to Section 7.3 and the eCRF completion guidelines for full instructions on the mechanism of pregnancy reporting.

The pregnancy itself is not considered an AE nor is an induced elective abortion to terminate a pregnancy without medical reasons.

Any premature termination of pregnancy (e.g. a spontaneous abortion, an induced therapeutic abortion due to complications or other medical reasons) must be reported within 24 hours as an SAE. The underlying medical reason for this procedure should be recorded as the AE term.

A spontaneous abortion is always considered to be an SAE and will be reported as described in Sections 7.1.1 and 7.1.2. Furthermore, any SAE occurring as an adverse pregnancy outcome post study must be reported to Gilead PVE.

The subject should receive appropriate monitoring and care until the conclusion of the pregnancy. The outcome should be reported to Gilead PVE using the pregnancy outcome report form. If the end of the pregnancy occurs after the study has been completed, the outcome should be reported directly to Gilead PVE. Gilead PVE contact information is as follows:

Email: PPD and Fax: PPD .

Pregnancies of female partners of male study subjects exposed to Gilead or other study drugs must also be reported and relevant information should be submitted to Gilead PVE using the pregnancy and pregnancy outcome forms within 24 hours. Monitoring of the subject should continue until the conclusion of the pregnancy. If the end of the pregnancy occurs after the study has been completed, the outcome should be reported directly to Gilead PVE, fax number PPD or email PPD

Refer to [Appendix 3](#) or Pregnancy Precautions, Definition for Female of Childbearing Potential, and Contraceptive Requirements.

7.7.2.2. Reporting Other Special Situations

All other special situation reports must be reported on the special situations report form and forwarded to Gilead PVE within 24 hours of the investigator becoming aware of the situation. These reports must consist of situations that involve study drug (including adalimumab) and / or other Gilead medications.

Special situations involving non-Gilead medications do not need to be reported on the special situations report form; however, for special situations that result in AEs due to a non-Gilead medication(s), the AE should be reported on the AE form.

Any inappropriate use of concomitant medications prohibited by this protocol should not be reported as “misuse,” but may be more appropriately documented as a protocol deviation.

Refer to Section [7.3](#) and the eCRF completion guidelines for full instructions on the mechanism of special situations reporting.

All clinical sequelae in relation to these special situation reports will be reported as AEs or SAEs at the same time using the AE eCRF and / or the SAE report form. Details of the symptoms and signs, clinical management, and outcome will be reported, when available.

8. STATISTICAL CONSIDERATIONS

8.1. Analysis Objectives and Endpoints

8.1.1. Analysis Objectives

Analysis objectives are aligned with the objectives specified in Section 2.

8.1.2. Primary Endpoint

The primary endpoint is listed in Section 3.1.1.

The primary null hypotheses are listed in Appendix 6.

8.1.3. Secondary Endpoints

The key secondary endpoints, other secondary CCI endpoints are listed in Sections 3.1.2 and 3.1.3.

The key secondary hypotheses are listed in Appendix 6.

8.2. Analysis Conventions

8.2.1. Analysis Sets

8.2.1.1. Efficacy

The primary analysis set for efficacy analyses will be the Full Analysis Set (FAS), which includes all randomized subjects who received at least one dose of study drug.

8.2.1.2. Safety

The primary analysis set for safety analyses will be the Safety Analysis Set, which includes all subjects who received at least one dose of study drug.

CCI

[REDACTED]

CCI

[REDACTED]

8.3. Data Handling Conventions

Values for missing safety laboratory data will not be imputed. If no baseline laboratory value is available, the baseline value will be assumed to be normal (i.e. no grade [Grade 0]) for the summary of graded laboratory abnormalities. If the safety laboratory results for a subject are missing for any reason at a time point, the subject will be excluded from the calculation of summary statistics for that time point.

Laboratory data that are continuous in nature but are less than the lower limit of quantitation or above the upper limit of quantitation will be imputed to the value of the lower or upper limit minus or plus one significant digit, respectively (e.g. if the result of a continuous laboratory test is <20, a value of 19 will be assigned; if the result of a continuous laboratory test is <20.0, a value of 19.9 will be assigned).

8.4. Demographic Data and Baseline Characteristics

Demographic and baseline measurements will be summarized using standard descriptive methods – 8-number summary (n, mean, SD, median, Q1, Q3, minimum, maximum) for continuous variables and the number and percentage of subjects per category for categorical variables.

Demographic summaries will include sex, race, ethnicity, and age.

Baseline characteristics will include randomization stratification factors, serum CRP, joint counts, HAQ-DI, and other variables of interest.

8.5. Efficacy Analysis

All continuous efficacy endpoints will be summarized using 8-number summary (n, mean, SD, median, Q1, Q3, minimum, maximum) by treatment group. All categorical efficacy endpoints will be summarized with the number and percentage of subjects who meet the endpoint or category definition by treatment group.

Besides the efficacy analyses specified in the protocol, sensitivity analyses may be performed for the efficacy assessments. More details on efficacy analyses will be described in the SAP.

8.5.1. Primary Analysis

8.5.1.1. Primary Estimand

The primary estimand corresponding to the treatment policy strategy is defined by the 4 attributes below:

- 1) Population: subjects in the FAS.
- 2) Variable / endpoint: binary ACR20 response variable at Week 12 indicating if a subject meets the ACR20 response criteria at Week 12.

- 3) Accounting for intercurrent events: include all on-study data regardless of protocol violations, use of rescue medication, change in background medication, and study drug discontinuation.
- 4) Population-level summary: the treatment difference in the percentage of subjects meeting ACR20 response criteria between each filgotinib group and the placebo group.

8.5.1.2. Main Estimator

A logistic regression analysis with treatment groups and stratification factors in the model will be used to analyze the primary endpoint. For subjects who do not have sufficient measurements to establish efficacy at Week 12, their data will be imputed using multiple imputation assuming that missing data are missing at random (MAR).

Sensitivity analyses to evaluate the robustness of results to violations of any assumptions made regarding the data missingness mechanisms will be specified in the SAP.

8.5.2. Secondary Analyses

8.5.2.1. Estimand

The main estimand corresponding to the treatment policy strategy for the key secondary endpoints is defined with the same attributes as in the primary estimand except that the variable / endpoint and population-level summary are endpoint specific. The key secondary endpoints are listed in Section 3.1.2. For the binary endpoints, the population-level summary is the treatment difference in the percentage of subjects meeting specified criteria for response between each filgotinib group and the placebo group. For the continuous endpoints, the population-level summary is the mean treatment difference between each filgotinib group and the placebo group.

8.5.2.2. Estimator

8.5.2.2.1. Superiority Test

For a superiority test of each filgotinib group compared to the placebo group on a binary efficacy endpoint, a logistic regression analysis with treatment groups and stratification factors in the model will be used.

For a superiority test of each filgotinib group compared to the placebo group on a continuous efficacy endpoint that is longitudinally collected, a mixed-effect model repeated measures (MMRM) analysis with treatment groups and stratification factors as fixed effects and subjects as a random effect in the model will be used. The model may also include visit, treatment-by-visit interaction, and the continuous baseline value as fixed effects.

8.5.2.2.2. Non-inferiority Test

The non-inferiority hypothesis based on the response rate of ACR20 at Week 12 ([Appendix 6](#)) will be tested using the 3-arm design approach proposed by [{Liu 2014}](#), which utilize the data collected from the placebo, filgotinib, and adalimumab groups. The traditional non-inferiority null hypothesis is $H_0: \pi_T - \pi_C \leq -\delta$ where: π_T is the response rate for the treatment group (i.e. filgotinib), π_C is the response rate for the active control group (i.e. adalimumab), and δ is the non-inferiority margin, where $\delta = (1 - \theta)(\pi_C - \pi_P)$ is usually estimated from historical data and π_P is the response rate for the placebo group. For the 3-arm design, the null hypothesis can be equivalently transformed to $H_0: \frac{\pi_T - \pi_P}{\pi_C - \pi_P} \leq \theta$. For this hypothesis testing, the response rates for the active control and placebo groups are estimated from the study data. A value of 0.5 is selected for θ , implying that the treatment is “at least as good as or non-inferior to” the active control [{Koch 1999}](#).

8.5.3. Hypothesis Testing Strategy

The graphical approach to sequentially rejective multiple test procedures ([Appendix 6](#) and [Appendix 7](#)) will be used to control a family wise type I error rate at 5% (i.e. $\alpha = 0.05$).

Within each filgotinib dosing regimen, the primary hypothesis will be first tested at $\alpha/2$. If the primary hypothesis is rejected, then the next secondary hypothesis in the same filgotinib dosing regimen will be tested at $\alpha/2$. Testing of the hypotheses happens sequentially in the same filgotinib dosing regimen. Once all hypotheses within the same filgotinib dosing regimen are rejected, then the respective $\alpha/2$ can be passed on to the other regimen’s hypotheses, that is, all hypotheses in the other filgotinib dosing regimen will be tested at α level.

The order of the key secondary hypotheses will be specified in the SAP.

8.6. Safety Analysis

All safety analyses will be performed using the Safety Analysis Set. Safety will be evaluated by assessments of clinical laboratory tests, physical examinations, vital signs measurements at various time points during the study, and by the documentation of AEs.

Safety endpoints will be summarized with the number and percentage of subjects with events or abnormalities for categorical values or 8-number summary (n, mean, SD, median, Q1, Q3, minimum, maximum) for continuous data by treatment group.

Two safety estimands, treatment policy and while on treatment, will be applied for the safety analysis.

In the analysis for the treatment policy estimand, all the safety data collected in the study will be included in the analysis. For while on treatment estimand, all the safety data collected up to 30 days after the last dose date of study drug will be included in the analysis. More details on safety analyses will be described in the SAP.

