6.5. Safety Follow-up Visit

The Safety Follow-up Visit will be performed approximately 4 weeks after a subject's last in-clinic visit in either the Main Study or the LTE as specified in the Study Procedures Table ([Appendix 2](#)). This visit should be done by phone call unless otherwise required by region.

Subjects in Europe will have additional Safety Follow-up Visits. These visits will occur 8, 12, and 16 weeks after their last SC injection of study drug and should also be done by phone call unless otherwise required by region. If the subject's last study visit is greater than or equal to 16 weeks from their last SC injection, the additional Safety Follow-up Visits will not be required.

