7.3. Investigator Requirements and Instructions for Reporting Adverse Events and Serious Adverse Events to Gilead

Requirements for collection prior to study drug initiation:

After informed consent, but prior to initiation of study medication, the following types of events should be reported on the eCRF: all SAEs and AEs related to protocol-mandated procedures.

Adverse Events

Following initiation of study medication, collect all AEs, regardless of cause or relationship, throughout the duration of the study, including at the protocol-required Safety Follow-up Visit must be reported to the eCRF database as instructed.

All AEs should be followed up until resolution or until the AE is stable, if possible. Gilead Sciences may request that certain AEs be followed beyond the protocol defined follow-up period.

Serious Adverse Events

All SAEs, regardless of cause or relationship, that occurs after the subject first consents to participate in the study (i.e. signing the informed consent) and throughout the duration of the study, including 30 days after last in clinic visit, must be reported to the eCRF database and Gilead PVE, as instructed. This also includes any SAEs resulting from protocol-associated procedures performed after informed consent is signed.

Investigators are not obligated to actively seek SAEs after the protocol defined follow-up period; However, if the investigator learns of any SAEs that occur after study participation has concluded and the event is deemed relevant to the use of study drug, he / she should promptly document and report the event to Gilead PVE.

- All AEs and SAEs will be recorded in the eCRF database within the timelines outlined in the eCRF completion guideline.

Electronic Serious Adverse Event (eSAE) Reporting Process

- Site personnel record all SAE data in the eCRF database and from there transmit the SAE information to Gilead PVE ≤ 24 hours of the investigator's knowledge of the event. Detailed instructions can be found in the eCRF completion guidelines.
- If for any reason it is not possible to record the SAE information electronically, i.e. the eCRF database is not functioning, record the SAE on the paper serious adverse event reporting form and submit ≤ 24 hours to:

Gilead PVE: Fax: PPD
E-mail: PPD

- As soon as it is possible to do so, any SAE reported via paper must be transcribed into the eCRF Database according to instructions in the eCRF completion guidelines.

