8.6.2. Adverse Events

Clinical and laboratory AEs will be coded using the MedDRA. System Organ Class, High-Level Group Term (HLGT), High-Level Term (HLT), Preferred Term (PT), and Lower-Level Term (LLT) will be attached to the clinical database.

Treatment-Emergent Adverse Events (TEAEs) are:

- Any AEs with an onset date of on or after the study drug start date and no later than the "analysis end date," which is defined separately for treatment policy estimand and while on treatment estimand as follows:

Treatment policy estimand: the latest date of either the last reported date in the study or 30 days after permanent discontinuation of study drug

While on treatment estimand: 30 days after permanent discontinuation of study drug

OR

- Any AEs leading to premature discontinuation of study drug.

Summaries (number and percentage of subjects) of TEAEs by System Organ Class and PT will be provided by treatment group. TEAEs will also be summarized by relationship to study drug and severity. In addition, TEAEs leading to premature discontinuation of study drug will be summarized and listed.

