Appendix 2. Study Procedures Table

EVENT		Part 1: Main Study								
		Screen (-28 days to 0)	Day 1	Weeks (±3 days)					ET (±7 days)	Safety Follow-up (±7 days) ^a
				2	4	8	12	16		
Visit (±window)										
Screening Assessments	Informed consent	X								
	Inclusion / Exclusion Criteria	X	X ^b							
	Demographics, Baseline / Disease Characteristics, PsA Diagnosis and Prior PsA Treatment, Medical History	X								
	Complete Physical Examination	X								
	TB Screening and Chest X-ray	X								
Patient Reported Outcomes	HAQ-DI: Health Assessment Questionnaire – Disability Index		X	X	X	X	X	X	X	
	FACIT-Fatigue: Functional Assessment of Chronic Illness Therapy – Fatigue Scale		X		X			X	X	
	SF-36v2: 36-item Short-Form Health Survey Version 2		X		X			X	X	
	PsAID-12: 12-item Psoriatic Arthritis Impact of Disease		X		X			X	X	
	CCI									
	CCI									
	CCI									
	CCI									
	PGADA: Patient’s Global Assessment of Disease Activity		X	X	X	X	X	X	X	
	PGAPI: Patient's Global Assessment of Psoriatic Arthritis Pain Intensity		X	X	X	X	X	X	X	

EVENT		Part 1: Main Study								
		Screen (-28 days to 0)	Day 1	Weeks (±3 days)					ET (±7 days)	Safety Follow-up (±7 days) ^a
				2	4	8	12	16		
Visit (±window)										
Physician Reported Outcomes	CASPAR: Classification Criteria for Psoriatic Arthritis	X								
	PASI including BSA: Psoriasis Area and Severity Index including Body Surface Area		X		X	X	X	X	X	
	mNAPSI: Modified Nail Psoriasis Severity Index		X		X	X	X	X	X	
	PhGAP: Physician's Global Assessment of Psoriasis		X	X	X	X	X	X	X	
	SPARCC Enthesitis Index and LEI: Spondyloarthritis Research Consortium of Canada Enthesitis Index and Leeds Enthesitis Index		X		X	X	X	X	X	
	SJC66 / TJC68: Swollen and Tender Joint Count	X	X	X	X	X	X	X	X	
	LDI: Leeds Dactylitis Index		X		X	X	X	X	X	
	PhGADA: Physician's Global Assessment of Disease Activity		X	X	X	X	X	X	X	
Safety	Vital Signs and Weight	X	X	X	X	X	X	X	X	
	Symptom-Driven Physical Examination		X	X	X	X	X	X	X	
	12-Lead ECG	X								
	Pregnancy Test ^c	X	X	X	X	X	X	X	X	X

EVENT		Part 1: Main Study								
		Screen (-28 days to 0)	Day 1	Weeks (±3 days)					ET (±7 days)	Safety Follow-up (±7 days) ^a
				2	4	8	12	16		
Visit (±window)										
Laboratory	Hematology and Chemistry	X	X	X	X	X	X	X	X	
	Urinalysis	X								
	Endocrine: FSH, TSH, and HbA1c ^d	X								
	Lipid profile (fasting)		X					X	X ^e	
	Serum CRP ^f		X	X	X	X	X	X	X	
	CCI									
	CCI									
	CCI									
	Biomarker Samples ^f		X	X	X		X	X		
	Viral Serology ^j	X								

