Birth control methods that are unacceptable include periodic abstinence (e.g. calendar, ovulation, symptothermal, post-ovulation methods), withdrawal (coitus interruptus), spermicides only, and lactational amenorrhea method (LAM). Female condom and male condom should not be used together.

5) Procedures to be Followed in the Event of Pregnancy

[figure not shown]
Subjects will be instructed to notify the investigator if they become pregnant at any time during the study, or if they become pregnant within 35 days of last study drug dose. Subjects who become pregnant or who suspect that they are pregnant during the study must report the information to the investigator and discontinue all the study drugs immediately. These subjects will be asked to continue in the study without taking study drug through the completion of the main study. Male subjects whose partner has become pregnant or suspects she is pregnant during the study or up to 90 days after the last dose of study drug are to report the information to the investigator.

Instructions for reporting pregnancy, partner pregnancy, and pregnancy outcome are outlined in Section 7.7.2.1.

6) Pregnancy Testing

All females of childbearing potential will have urine pregnancy testing every 4 weeks during the dosing period through the Safety Follow-up Visit (28-35 days after their last dose of study drug). During the periods where study visits are every 6-8 weeks, women should continue to have pregnancy tests every 4 weeks, using home pregnancy urine tests that will be provided to them. The site will call the subject every 4 weeks to obtain results of these pregnancy tests and will record the information in the source documents and eCRF. If a positive urine pregnancy test is reported, the subject will be asked to return to the clinic for a confirmatory serum pregnancy test.

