7.1.5. Treatment-Emergent Adverse Events

7.1.5.1. Definition of Treatment-Emergent Adverse Events

Treatment-emergent adverse events (TEAEs) are defined as one or both of the following:

- Any AEs with an onset date on or after the study drug start date and no later than 30 days after permanent discontinuation of study drug
- Any AEs leading to premature discontinuation of study drug.

For subjects who entered LTE, TEAEs with an onset date prior to first dose date of any study drug for LTE will be allocated to the Main Study phase. TEAEs with an onset date on or after the first dose date of any study drug for LTE will be allocated to the LTE phase.

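### Collection of non-serious adverse events can close before the 30-day TEAE window ends, by up to 9 days when the last dose and the last clinic visit coincide

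*Protocol*

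**What the plan says.** **The counting window.** Protocol Section 8.6 takes into the while-on-treatment safety analysis "all the safety data collected up to 30 days after the last dose date of study drug". Section 8.6.2 gives the matching end date for treatment-emergent events: "While on treatment estimand: 30 days after permanent discontinuation of study drug". SAP 7.1.5.1 keeps this limit, counting events with onset "no later than 30 days after permanent discontinuation of study drug". SAP 7.6 drops the treatment-policy safety analysis, so this is the only TEAE definition that will be summarized.

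**The collection window.** Protocol Section 7.3 requires all AEs, serious or not, to be collected "throughout the duration of the study, including at the protocol-required Safety Follow-up Visit". SAEs alone have a separate fixed limit in that section: 30 days after the last in-clinic visit.

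**The timing of the contact.** Section 6.5 states: "The Safety Follow-up Visit will be performed approximately 4 weeks after" the subject's "last in-clinic visit in either the Main Study or the LTE". Section 3.2 likewise says four weeks after the final visit. The column heading in Appendix 2 adds the tolerance: "Safety Follow-up (±7 days", with the bracket then closed. Appendix 3 item 6, on pregnancy testing, dates the same visit differently: "Safety Follow-up Visit (28-35 days after their last dose of study drug", bracket again closed. Section 6.5 gives European subjects further contacts 8, 12 and 16 weeks after the last injection, unless their last study visit already falls 16 weeks or more after it.

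**The concern.** The counting window runs from the last dose and lasts 30 days. The contact that ends collection of non-serious events runs from the last clinic visit and may fall as early as 21 days after it. Nothing in the protocol requires the contact to fall at or after Day 30 from the last dose. A site can therefore call within its permitted window, close the AE record, and leave the last days of the counting window unobserved for non-serious events.

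The loss can go in one direction only: events are missed, never added. A reader of the TEAE tables would naturally assume 30 days of complete follow-up after treatment. The two statements of the visit's timing also differ in anchor (last visit against last dose) and in lower limit (21 against 28 days), so sites cannot tell which one governs.

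**Working it through.** **Inputs**

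- Counting window: 30 days after last dose (Protocol 8.6, 8.6.2; SAP 7.1.5.1).
- Nominal contact: 4 weeks = 28 days after the last in-clinic visit (Protocol 6.5).
- Tolerance: ±7 days (Appendix 2).
- L = days from last dose to last in-clinic visit. The documents do not give it, so it is varied below.

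**Formulas**

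- Contact day after last dose = 28 ± 7 + L.
- Unobserved tail = max(0, 30 − contact day).

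**The plan's own figure.** Appendix 3 gives 28 to 35 days after last dose. With L = 0, Section 6.5 and Appendix 2 give 28 − 7 = 21 to 28 + 7 = 35. The upper limit agrees; the lower limit does not (21, not 28).

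**Size of the gap**

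| L (days) | Contact day after last dose | Largest tail | Tail if call exactly on time |
|---|---|---|---|
| 0 | 21 to 35 | 30 − 21 = 9 | 30 − 28 = 2 |
| 1 | 22 to 36 | 8 | 1 |
| 2 | 23 to 37 | 7 | 0 |
| 7 | 28 to 42 | 2 | 0 |
| 9 | 30 to 44 | 0 | 0 |

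The gap falls by one day per day of L and is excluded once L reaches 30 − 21 = 9. If Appendix 3 governs, the largest tail is 30 − 28 = 2 days.

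**How large L can be under the protocol.** In the LTE, the early termination visit is due within 7 days of stopping study drug (Section 6.3.2), so a visit on schedule never reaches L = 9. The Main Study rule is 7 days from leaving the study (Section 6.3.1), which has the same effect for subjects who stop drug and study together. Subjects who stop drug early but attend to Week 16 (Section 3.5.2) can have L well above 9, and then there is no gap.

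**SAEs.** Collection runs to 30 days after the last in-clinic visit, so the 30 days after last dose are covered whenever that visit is on or after the last dose.

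**Europe.** Take a subject leaving at Week 16 with the last injection at about Week 14 and the last tablet 14 days later. The 8-week call is 56 − 14 = 42 days after the last tablet, or 42 − 7 = 35 if a call 7 days early is allowed. Both exceed 30. This reads the extra Safety Follow-up contacts as also collecting AEs.

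**Scale against the whole window.** TEAEs count from first dose. For a subject dosed to nominal Day 113 (Week 16), the window is 113 + 30 = 143 days. A 9-day tail is 9/143 = 6.3% of it, and a 2-day tail is 2/143 = 1.4%.

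**The case against.** The strongest reply is that Section 8.6 sets a cap on which collected data are included and makes no promise that 30 days are fully observed. The same cap applies in every arm, region is a stratification factor, and the AE tables count each subject once per summary, so a few lost days need not cost a proportionate share of incidence. The trial also stopped after 67 subjects (SAP 1.3). All of this stands. It limits the consequence to a slight under-count, with no demonstrated bias between arms. It does not remove the mismatch.

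A reader might go further and infer that the window is usually incomplete. Two routes to that reading are tempting, and the documents support neither.

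- *Most contacts come too early.* If L = 0 for everyone and calls were spread evenly over the 15 permitted days, 9/15 = 60% would precede Day 30, with a mean loss of 45/15 = 3 days. The documents give neither the spread of calls nor L. Under the same even spread the share is 2/15 = 13% at L = 7 and nil from L = 9, so anything from 0 to 60% is possible. The figure also ignores the later European contacts; Bulgaria, Poland and Spain are among the countries in SAP 3.3.
- *Most subjects are affected.* SAP 1.3 implies that 67 − 13 = 54 of 67 subjects did not enter the LTE. That is only a ceiling. For subjects enrolled under Protocol Amendment 1 who stayed in the Main Study past Week 16, SAP Section 3 summarizes data only to the Week 16 visit, and their number is not given. Others may have stopped drug well before their last visit.

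**Conclusion.** The mismatch is real and of low severity. Non-serious AE collection can end before the 30-day TEAE window does. The shortfall is 0 to 9 days when last dose and last visit fall on the same day, 2 days when the call is exactly on time, and at most 2 days if Appendix 3 governs. It disappears once the last visit is 9 or more days after the last dose. SAEs are not affected when the last visit is on or after the last dose. European subjects leaving in or soon after the Main Study have later contacts that cover the window.

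The documents do not show how often the gap occurs, so no statement of frequency is warranted. The expected effect is a small under-count of late non-serious events, under a rule common to all arms.

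**What to change.** 1. Reconcile Section 6.5, Appendix 2 and Appendix 3 item 6 so that the Safety Follow-up contact has one stated anchor and one window.
2. Keep the contact tied to the last in-clinic visit, and add that it may not take place earlier than 30 days after the last dose of any study drug. The unobserved tail is then zero for every L.
3. Do not anchor it to the last dose alone. A window of 30 to 37 days after last dose would, for a subject who stopped at Week 4 (Day 29), close AE collection on Days 59 to 66, while that subject is still attending visits to Week 16 (Day 113).
4. For subjects already followed, list or footnote beside the TEAE table those whose AE collection ended before Day 30 after last dose, or state that the final days are observed for SAEs only. SAP Section 1 allows later changes to be documented in the clinical study report.

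The cost of the protocol change is a phone call made somewhat later for some subjects, by 9 days at most. Items 1 to 3 matter if the protocol text is used again. For this terminated trial the useful step is item 4, which needs only the last-dose and follow-up contact dates.
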